1. PROTOCOL SYNOPSIS FOR STUDY 201810

Rationale

The efficacy of mepolizumab in severe asthma has been demonstrated over one year of continuous treatment in double-blinded studies. However, it is currently unknown whether chronic exposure is necessary for disease control. It was recently reported that discontinuation of mepolizumab after one year of treatment resulted in the increased presence of eosinophils and a corresponding increase in exacerbation frequency to pre-study levels, suggesting that a treatment response was not sustained after treatment discontinuation. Beyond one year of treatment, there is no data available on the sustainability of a treatment response following the discontinuation of mepolizumab.

Asthma management guidelines recommend stepping down therapy once control is achieved in an effort to find the patient's minimal effective treatment. Thus, it remains important to understand the duration of response to mepolizumab when treatment is withdrawn after longer-term exposure.

Objectives

Primary Objective

To evaluate whether patients with severe eosinophilic asthma who have received long-term treatment with mepolizumab (at least 3 years) need to maintain treatment with mepolizumab to continue to receive benefit.

Secondary Objective

To assess the safety and tolerability of mepolizumab continuation compared to placebo following long-term treatment with mepolizumab in patients with severe eosinophilic asthma.

Endpoints

Primary Endpoint

- Time to first clinically significant exacerbation

Clinically significant exacerbations will be defined as worsening of asthma which requires use of systemic corticosteroids¹ and/or hospitalisation and/or emergency department (ED) visits.

¹For all subjects, i.v. or oral corticosteroid (e.g., prednisone) for at least 3 days or a single intramuscular (IM) corticosteroid dose is required. For subjects on maintenance systemic corticosteroids, at least double the existing maintenance dose for at least 3 days is required.

Secondary Endpoints

- Ratio to baseline in blood eosinophil count at weeks 12, 24, 36 and 52
- Time to a decrease in asthma control, defined as an increase from baseline in Asthma Control Questionnaire-5 (ACQ-5) score of ≥ 0.5 units
- Time to first exacerbation requiring hospitalization or ED visit

Other Endpoints

- Time to first exacerbation requiring hospitalization
- Mean change from baseline in clinic pre-bronchodilator FEV₁ at weeks 12, 24, 36, 52
- Mean change from baseline in clinic post-bronchodilator FEV₁ at weeks 12, 24, 36, 52
- Mean change from baseline in daily salbutamol/albuterol use
- Mean change from baseline in daily asthma symptom scores
- Mean change from baseline in awakening at night due to asthma symptoms requiring rescue medication use
- Mean change from baseline in morning (AM) Peak Expiratory Flow (PEF)
- Time to worsening of asthma (subjects meeting at least 2 of the following 4 criteria for worsening of asthma for at least 2 consecutive days)
 - **AM PEF:** Decrease in AM PEF $\geq 30\%$ compared with baseline (last 7 days of run-in Part B).
 - **Rescue Medication Use:** An increase of $\geq 50\%$ in rescue medication compared with the average use for the previous week.
 - **Night time awakenings requiring rescue medication:** Awakening due to asthma symptoms requiring rescue medication
 - **Symptoms:** An asthma symptom score of 5
- Mean change from baseline in ACQ-5 score
- Proportion of patients experiencing a decrease in asthma control, defined as an increase from baseline in ACQ-5 score of ≥ 0.5 or more units
- Proportion of subjects with a clinically meaningful worsening of health-related quality of life measurements (St. George's Respiratory Questionnaire, SGRQ) at weeks 12, 24, 36 and 52 (defined as subjects who have a clinically relevant increase from baseline of ≥ 4 units in SGRQ score).
- Mean change from baseline in SGRQ score at week 12, 24, 36 and 52
- Subject/Clinician global impression of asthma severity rating at weeks 12, 24, 36 and 52

- Subject/Clinician rating of response to therapy at weeks 12, 24, 36 and 52
- Number of days in hospital due to asthma
- Unscheduled healthcare contacts/resource utilisation
- Days off of regular work/school

Safety Endpoints

- Adverse Events and Serious Adverse Events
- Clinical Laboratory parameters
- 12-lead ECG parameters
- Vital Signs

Overall Design

This is a 52-week, 2-arm, randomized, double-blind, parallel-group, multi-center study evaluating mepolizumab 100 mg and placebo administered subcutaneously (SC) every 4 weeks in subjects with severe eosinophilic asthma who have been treated with mepolizumab continuously in addition to standard of care therapy for at least 3 years. Subjects who participated in the open-label studies MEA115666 or 201312 and who have no treatment gaps of more than 12 weeks (84 days) between any two doses of mepolizumab in MEA115666 or 201312, will be eligible to participate in this study.

It is intended that the Follow up/Exit Visit or Early Withdrawal (EW) Visit for studies MEA115666 and 201312 will serve as the Pre-Screening/Screening Visit (Visit 0/Visit 1) for this study.

Part A and B: Variable and Fixed Open-Label Run-In Periods

At Visit 1 (Screening), eligible subjects will have their exposure period for mepolizumab treatment assessed:

- **Subjects with less than 3 years of mepolizumab treatment** will enter Part A of the study, a variable open-label run-in period on mepolizumab (100 mg SC every 4 weeks) of 4 to 132 weeks, in order for subjects to reach 3 years of exposure to mepolizumab.
 - Once the required 3 year exposure is reached, the subject will enter Part B of the study at Visit B1 and complete a fixed run-in period of 4 weeks (up to 8 weeks) during which open-label mepolizumab (100 mg SC every 4 weeks) is administered, in order to collect baseline information.

- **Subjects with at least 3 years of mepolizumab treatment** will directly enter Part B of the study. For these subjects, assessments for Visit 1 and Visit B1 should be conducted on the same day. No assessments should be duplicated.

Part C: Double-Blind Treatment Period

Upon completion of the fixed run-in period Part B, eligible subjects will be randomized 1:1 to the following double-blinded treatment arms at Visit C1:

- mepolizumab (100 mg) administered SC every 4 weeks
- placebo administered SC every 4 weeks

Part D: Optional Switch to Open-Label Mepolizumab

Subjects who experience a clinically significant asthma exacerbation during the double-blind treatment period Part C will require a prompt assessment by the investigator to determine if they should continue taking double-blind study treatment.

Subjects deemed to be unsuitable to continue double-blind study treatment by the Investigator should discontinue double-blind investigational product (IP) and complete a Discontinuation of IP Visit approximately 4 weeks following their last dose of double-blind IP.

Subjects discontinuing IP due to a clinically significant asthma exacerbation are eligible to enter optional Part D of the study and receive open-label mepolizumab in addition to their standard of care therapy for the remainder of the study, through Part D, to Visit D13. Subjects switching to Part D should complete the Discontinuation of IP Visit and their first Part D visit on the same day, corresponding to the week post-randomization. No assessments should be duplicated.

Switch to Part D between visits: For example, if a subject completed Visit C7 at Week 24 (and the subject received a dose of IP at Visit C7) and it is later determined that they should switch to Part D, the IP Discontinuation assessments and the first visit in Part D will be D8 at Week 28.

Switch to Part D during a visit: If a subject is in the process of completing a Part C visit, as long as they have not yet received a dose of IP, they may be switched to Part D at that same visit (e.g., a subject that is part way through Visit C7 at Week 24 and whose last dose of IP was at Visit C6, Week 20 can be switched to Part D and complete the IP Discontinuation assessments and Visit D7 at that same visit, Week 24).

An Exit Visit will be conducted 52 weeks after randomization (whether the subject is in Part C or Part D) in order to assess subject's efficacy parameters, immunogenicity status, and to conduct additional safety assessments.

Subjects who permanently discontinue study treatment in Part C or D of the study are NOT required to withdraw from the study. If a subject discontinues double blind study treatment during Part C and does not switch to Part D at their next visit (IP

Discontinuation Visit) after experiencing a clinically significant asthma exacerbation, the subject cannot enter Part D at a later visit.

Treatment Arms and Duration

Eligible subjects will participate in the study ranging from 56 to 192 weeks, depending on the duration of Part A (0 to 132 weeks) and Part B (4 to 8 weeks). A summary of study phases is described in [Table 1](#).

Table 1 Study Phases, Duration and Study Treatments

Study Phase	Phase Title	Duration	Treatment arms
Part A	Variable Open-Label Run-in	0 to 132 weeks	Open-label mepolizumab (100 mg SC) every 4 weeks
Part B	Fixed Open-Label Run-In	4 weeks (up to 8 weeks)	Open-label mepolizumab (100 mg SC) every 4 weeks
Part C	Double Blind Treatment Period	52 weeks	Subjects randomized 1:1 to double-blind study treatment: 
 • mepolizumab (100 mg SC) every 4 weeks • placebo administered SC every 4 weeks
Optional Part D	Open-Label Switch	Up to 52-weeks post-randomization	Open-label mepolizumab (100 mg SC) every 4 weeks

Type and Number of Subjects

Subjects with severe eosinophilic asthma who completed the Follow Up/Exit Visit or EW Visit from either open-label study MEA115666 or 201312 will be eligible to participate in this study.

Approximately 375 subjects from studies MEA115666 and 201312 are expected to be screened in order for approximately 300 subjects to be randomized 1:1 to double-blind study treatment (150 per arm).

Sample Size and Analysis

With a sample size of 300 randomized subjects (150 per arm), it is estimated that statistical significance will be declared if the proportion of subjects with a clinically significant exacerbation following withdrawal of mepolizumab is 52.5% compared to 40% for those continuing to receive mepolizumab (hazard ratio = 0.686).

If the true hazard ratio is 0.55 (corresponding to a proportion with a clinically significant exacerbation following discontinuation of mepolizumab of 60.5%), then the study has a probability of 90% of observing a hazard ratio of < 0.686 and therefore the study has 90% power for declaring statistical significance on this endpoint.

Time to first clinically significant exacerbation will be compared between treatment groups using a Cox's proportional hazards model allowing for covariates of region, exacerbations in the year prior to randomization and use of baseline maintenance oral corticosteroids (OCS vs no OCS).

2. INTRODUCTION

Eosinophilic inflammation of the airways specifically plays a central role in the pathogenesis of asthma [Cohn, 2004]. Eosinophils are not normally present in healthy lungs, and are thought to play a major role in maintaining airway inflammation [Walsh; 2010; Wadsworth, 2011]. Studies in the severe asthma population have shown that more than half of these patients have persistent eosinophilic (>3% eosinophils) airway inflammation despite corticosteroid therapy [Wenzel, 2005; ENFUMOSA, 2003].

Of the inflammatory mediators postulated to contribute to the regulation of eosinophil trafficking and degranulation, interleukin-5 (IL-5) has been identified as the main cytokine to selectively regulate eosinophil function [Sumitas, 2011]. IL-5 specifically promotes the differentiation of eosinophils in the bone marrow and stimulates the release of eosinophils from the bone marrow into peripheral circulation [Sanderson, 1992; Collins, 1995]. Binding of IL-5 to eosinophil-expressing IL-5 receptors results in enhanced adhesion of eosinophils to endothelial cells and increased eosinophil survival and activation [Lopez, 1988].

Mepolizumab is a humanized anti-interleukin 5 (anti-IL5) antibody (IgG Kappa) that binds to and inactivates IL-5. Mepolizumab is currently under clinical development for the treatment of severe asthma.

2.1. Study Rationale

The efficacy of mepolizumab in severe asthma has been demonstrated over one year of continuous treatment in double-blinded studies. However, it is currently unknown whether chronic exposure is necessary for disease control. It was recently reported that discontinuation of mepolizumab after one year of treatment resulted in the increased presence of eosinophils and a corresponding increase in exacerbation frequency to pre-study levels, suggesting that a treatment response was not sustained after treatment discontinuation [Haldar, 2014]. Beyond one year of treatment, there is no data available on the sustainability of a treatment response following the discontinuation of mepolizumab.

Asthma management guidelines recommend stepping down therapy once control is achieved in an effort to find the patient's minimal effective treatment [GINA, 2015]. Thus, it remains important to understand the duration of response to mepolizumab when treatment is withdrawn after longer-term exposure.

2.2. Brief Background

Mepolizumab binds with high affinity to human IL-5 and blocks its binding to and the activation of the IL-5 receptor (CD125).

The randomized, multi-centre, placebo-controlled exacerbation studies (MEA112997, MEA115588) and Oral Corticosteroid (OCS) Reduction Study (MEA115575) have demonstrated the efficacy of mepolizumab and support the use of mepolizumab 100 mg

SC every 4 weeks as an add-on therapy for the treatment of severe eosinophilic asthma. Compared with placebo, mepolizumab has been shown to:

- Reduce the rate of clinically significant exacerbations by approximately 50%. These results were replicated in studies MEA112997 and MEA115588.
- Reduce the rate of exacerbations requiring hospitalisations and/or Emergency Department (ED) visits, with mean reductions ranging from 32% to 61%.
- Produce statistically significant and/or clinically relevant improvements in lung function based on forced expiratory volume in one second (FEV₁), asthma control based on Asthma Control Questionnaire (ACQ-5), quality of life based on St. George's Respiratory Questionnaire (SGRQ) and clinician and subject-rated overall response to therapy in the target population.
- Produce consistent reductions in blood eosinophil levels detected at Week 4 which were sustained for the duration of treatment.

Additional details of the pharmacology, efficacy and safety can be found in the Investigator Brochure (IB).

3. OBJECTIVES

3.1. Primary Objective

To evaluate whether patients with severe eosinophilic asthma who have received long-term treatment with mepolizumab (at least 3 years) need to maintain treatment with mepolizumab to continue to receive benefit.

3.2. Secondary Objective

To assess the safety and tolerability of mepolizumab continuation compared to placebo following long-term treatment with mepolizumab in patients with severe eosinophilic asthma.

4. ENDPOINTS

Primary Endpoint

- Time to first clinically significant exacerbation

Clinically significant exacerbations will be defined as worsening of asthma which requires use of systemic corticosteroids¹ and/or hospitalisation and/or ED visits.

¹For all subjects, i.v. or oral corticosteroid (e.g., prednisone) for at least 3 days or a single intramuscular (IM) corticosteroid dose is required. For subjects on maintenance systemic corticosteroids, at least double the existing maintenance dose for at least 3 days is required.

Secondary Endpoints

- Ratio to baseline in blood eosinophil count at weeks 12, 24, 36 and 52
- Time to a decrease in asthma control, defined as an increase from baseline in Asthma Control Questionnaire-5 (ACQ-5) score of ≥ 0.5 units
- Time to first exacerbation requiring hospitalization or ED visit

Other Endpoints

- Time to first exacerbation requiring hospitalization
- Mean change from baseline in clinic pre-bronchodilator FEV₁ at weeks 12, 24, 36, 52
- Mean change from baseline in clinic post-bronchodilator FEV₁ at weeks 12, 24, 36, 52
- Mean change from baseline in daily salbutamol/albuterol use
- Mean change from baseline in daily asthma symptom scores
- Mean change from baseline in awakening at night due to asthma symptoms requiring rescue medication use
- Mean change from baseline in morning (AM) Peak Expiratory Flow (PEF)
- Time to worsening of asthma (subjects meeting at least 2 of the following 4 criteria for worsening of asthma for at least 2 consecutive days)
 - **AM PEF:** Decrease in AM PEF $\geq 30\%$ compared with baseline (last 7 days of run-in Part B)
 - **Rescue Medication Use:** An increase of $\geq 50\%$ in rescue medication compared with the average use for the previous week
 - **Night time awakenings requiring rescue medication:** Awakening due to asthma symptoms requiring rescue medication
 - **Symptoms:** An asthma symptom score of 5
- Mean change from baseline in ACQ-5 score
- Proportion of patients experiencing a decrease in asthma control, defined as an increase from baseline in ACQ-5 score of ≥ 0.5 units
- Proportion of subjects with a clinically meaningful worsening of health-related quality of life measurements (SGRQ) at weeks 12, 24, 36 and 52 (defined as subjects who have a clinically relevant increase from baseline of ≥ 4 units in SGRQ score).
- Mean change from baseline in SGRQ score at week 12, 24, 36 and 52
- Subject/Clinician global impression of asthma severity rating at weeks 12, 24, 36 and 52

- Subject/Clinician rating of response to therapy at weeks 12, 24, 36 and 52
- Number of days in hospital due to asthma
- Unscheduled healthcare contacts/resource utilisation
- Days off of regular work/school

Safety Endpoints

- Adverse Events and Serious Adverse Events
- Clinical Laboratory parameters
- 12-lead ECG parameters
- Vital Signs

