#### 5.2.1.2. Part C Baseline Definition

- The Part C baseline will be defined for all subjects who are within the ITT (Part C) population.
- For endpoints collected outside of the eDiary and Asthma Control Questionnaire (ACQ-5) collected in the eDiary the Part C baseline values for each assessment will be the latest available assessment prior to first dose of double-blind treatment (however no earlier than the first dose of open-label mepolizumab), including data from unscheduled visits.
- Measurements on the same date as the first administration of double-blind treatment will be considered within the baseline derivation if measurement time is not captured. Where the measurement time is captured this should be compared against the time of first receiving double-blind treatment.
- For data collected via the eDiary device (i.e. morning peak flow, usage of rescue medication [i.e. salbutamol/albuterol], asthma symptom score and frequency of awakening due to asthma symptoms), the Part C baseline for analyses of averaged 4-weekly data will be calculated as an average using values over 7 days (immediately

prior and including the first dose of double-blind treatment), see Section 11.3.5 for further details.

- The current smoking status at Visit C1 will be derived from the responses obtained at Screening and Visit C1 (where changes in smoking status are collected, See Section 11.6.2).

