#### 7.3.2.1. Statistical Methodology Specification

Endpoint / Variables

 
• Time to first exacerbation requiring hospitalization (ADaM Dataset: ADTTE)
 
• Time to worsening of asthma (subjects meeting at least 2 of the following 4 criteria for worsening of asthma for at least 2 consecutive days) (ADaM Dataset: ADTTE):               
 
○ AM PEF: Decrease in AM PEF <math>\geq 30\%</math> compared with Part C baseline
 
○ Rescue Medication Use: An increase of <math>\geq 50\%</math> in rescue medication compared with the average use for the previous week
 
○ Night time awakenings requiring rescue medication: Awakening due to asthma symptoms requiring rescue medication
 
○ Symptoms: An asthma symptom score of 5
 
 
 

 
• Time to first event within Part C will be derived relative to the date of first dose of double-blind treatment [see Section 11.6.1, Part C study day].
 
• For consistency, exacerbations separated by less than 7 days will be treated as a continuation of the same exacerbation (see Section 11.6.3).
 
• See Section 5.2 for further details regarding baseline and change from baseline derivations.
 
• See Section 11.6.3 for details regarding eDiary data and Section 11.3.5 regarding visit windowing.
 
• In the analysis of Time to worsening of asthma only non-missing measurements indicative of asthma worsening (per above endpoint definition) will be considered as an event. Intermediate missing responses in a subject's eDiary data will be assumed to be missing at random, and will not be considered to indicate a worsening of their asthma.
 
• See Section 11.7.2 for further details on handling missing/partial data.
 

Summary Measure

 
• The hazard ratio (Mepolizumab 100mg SC / Placebo) will be the summary measure used for the treatment comparison.
 

Strategy for Intercurrent (Post-Randomization) Events

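### Time to worsening of asthma: the rescue-use criterion is measured against the previous week, so a slow rise or a plateau does not meet it and the hazard ratio is likely to be diluted

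*Protocol*

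**What the plan says.** Protocol 4 lists time to worsening of asthma among the other endpoints. An event is defined by "subjects meeting at least 2 of the following 4 criteria for worsening of asthma for at least 2 consecutive days". The four criteria use different kinds of reference:

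- **AM PEF** (a fall of at least 30%): fixed, "compared with baseline (last 7 days of run-in Part B" in the Protocol and "compared with Part C baseline" in SAP 7.3.2.1.
- **Rescue use** (a rise of at least 50%): moving, "in rescue medication compared with the average use for the previous week". SAP 2.3.3 and 7.3.2.1 keep this reference.
- **Night awakening**: absolute, "Awakening due to asthma symptoms requiring rescue medication".
- **Symptoms**: absolute, "An asthma symptom score of 5".

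SAP 7.3.2.1 analyses the endpoint with the primary Cox model and reports a hazard ratio, confidence interval and p-value (Table 2.46, Figure 2.17). It plans no analysis with a fixed rescue reference. Neither document says what a 50% increase means when the previous week's average is zero.

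A fixed eDiary baseline already exists. SAP 5.2.1.2 states that "the Part C baseline for analyses of averaged 4-weekly data will be calculated as an average using values over 7 days" ending on the day of the first double-blind dose, and SAP 11.3.5 gives the window.

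**The concern.** With a previous-week reference, the comparator rises along with the deterioration. Use that climbs slowly after withdrawal is always compared with a week that was almost as bad. Use that has settled at a higher level is compared with itself. Gradual return is a pattern worth planning for, since Protocol 10.2.1 expects earlier mepolizumab treatment to have continuing effects in the withdrawal arm.

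The two-day, two-criterion rule narrows the window further. A second criterion that appears after the rescue rise has been absorbed into its own reference can no longer pair with it. At stake is whether the reported hazard ratio understates the difference between stopping and continuing, and whether one quarter of the composite responds to short-term fluctuation more than to worsening from baseline.

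**Working it through.** **Plan figure.** The documents give no event rate, effect size or power for this endpoint, so there is no planned figure to reproduce. The rule itself can be evaluated directly as: today's use ≥ 1.5 × mean use over the previous 7 days.

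**1. Step rise (no rate assumptions).** Let use go from 1 to f and stay there. On day k the previous-week mean is ((8 − k) + (k − 1)f)/7 for k up to 8, so the criterion is 7f ≥ 1.5((8 − k) + (k − 1)f).

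| Day | Condition | f needed |
|---|---|---|
| 1 | 7f ≥ 10.5 | 1.50 |
| 2 | 5.5f ≥ 9 | 1.64 |
| 3 | 4f ≥ 7.5 | 1.875 |
| 4 | 2.5f ≥ 6 | 2.4 |
| 5 | f ≥ 4.5 | 4.5 |
| 6 | −0.5f ≥ 3 | none |

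A step of at least 64% therefore meets the two-day requirement. A step of 50% to 63% meets it on day 1 only and fails. A doubling qualifies on days 1–3 and a tripling on days 1–4. No step qualifies beyond day 5.

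**2. Straight-line rise (no rate assumptions).** For a doubling over 84 days, use on day t is 1 + t/84. The highest ratio to the previous week is on day 7: (1 + 7/84)/(1 + 3/84) = 91/87 = 1.05. Against a fixed baseline the criterion is met once t/84 ≥ 0.5, from day 42 to day 364, which is 323 days.

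| Rise | Peak ratio to previous week | Days met, previous week | Days met, fixed baseline |
|---|---|---|---|
| ×2 over 7 days | 1.42 | 0 | 361 |
| ×2 over 84 days | 1.05 | 0 | 323 |
| ×3 over 14 days | 1.42 | 0 | 361 |
| ×3 over 84 days | 1.09 | 0 | 344 |
| ×4 over 28 days | 1.34 | 0 | 360 |
| ×8 over 28 days | 1.66 | 6 | 363 |

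Constant proportional growth must reach about 11.3% a day (doubling in about 6.5 days) to qualify.

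**3. Chance days (assumption: Poisson daily use).** At a stable 1, 2 or 3 occasions a day, the previous-week rule is met on 0.30, 0.27 and 0.22 of days. It is met less often as use rises. Against a baseline taken at 1 a day, the figures are 0.30, 0.59 and 0.79.

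**4. Whole endpoint (simulation; all rates assumed).** Poisson use over 364 days, starting at 0.5 or 2 occasions a day, all four criteria. Mepolizumab is unchanged and placebo changes as shown. Hazard ratios are mepolizumab/placebo, for a start of 0.5 and of 2 a day.

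| Placebo change | Previous week | Fixed baseline |
|---|---|---|
| Rescue ×2 only | 1.12, 1.07 | 0.94, 0.80 |
| Rescue ×2, awakenings ×1.5 | 0.93, 1.01 | 0.70, 0.63 |
| Rescue ×2, awakenings ×2 | 0.72, 0.89 | 0.51, 0.48 |
| Rescue ×2, acute episodes ×2 | 0.64, 0.56 | 0.57, 0.48 |
| All three ×2 | 0.50, 0.50 | 0.40, 0.35 |

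The previous-week rule is nearer to 1, or beyond it, in every row. Other assumed rates put the first row's scenario anywhere from 0.75 to 1.8, so even there the direction depends on the model.

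**The case against.** The strongest defence is that the endpoint was built for acute change. Its thresholds closely follow the eDiary alerts in Protocol 8.3.2.2.1, which use the same previous-week reference for rescue use, and a recent reference suits an acute event. Protocol 5.4 gives the task of showing return of disease activity to the primary endpoint.

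Sustained worsening is also covered elsewhere. "Mean change from baseline in daily salbutamol/albuterol use" is a separate endpoint, summarised by 4-week period against the Part C baseline (SAP 7.3.3, Table 2.42). Symptoms, awakenings and PEF are treated the same way (Tables 2.43–2.45). Time to an ACQ-5 rise of at least 0.5 from baseline is a secondary endpoint. Time to worsening of asthma itself is exploratory, carries no power claim and cannot change the trial's main conclusion.

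All of this stands, and it is why the point is minor. It does not remove the point. The 4-weekly outputs are descriptive and do not correct a hazard ratio that will be reported with a p-value, and PEF within the same composite already has a fixed reference.

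A further objection is to the remedy: when the reference mean is at or below 1/1.5 = 0.67 a day, one rescue-requiring awakening meets two criteria at once. That is true, but it applies equally to the previous-week rule.

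**Conclusion.** The moving reference is in both documents, and the results for steps and straight-line rises are pure arithmetic. The rescue criterion catches an abrupt rise of at least 64% for up to five days. It misses a doubling spread over a week or more, a tripling spread over two weeks or more, and any later plateau. Dilution of the hazard ratio is the likely consequence. For example, it is 0.72 instead of 0.51 when rescue use and awakenings both double from a start of 0.5 a day. That size depends on assumed use, awakening and episode rates, because the documents give none.

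A reader might infer that any sustained rise cancels itself out, or that the endpoint will favour the arm that got worse. The documents do not support either. This is a time-to-first endpoint, so detection at onset is enough if a second criterion coincides. Any two of the other three criteria give an event without rescue use. In the tabulated scenarios, clear reversal appeared only when rescue use drifted up with flat awakenings and no excess of acute episodes. Nothing in the plan predicts that combination: Protocol 10.2.1 speaks only of a lower event rate from continuing effects of earlier treatment. Severity: minor.

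**What to change.** In SAP 7.3.2.1, add a second derivation of the rescue criterion: an increase of at least 50% over the 7-day Part C eDiary baseline mean. Report the Cox hazard ratio under that reference, at least as a prespecified sensitivity analysis beside the previous-week version. Say explicitly that the 7-day mean applies here, because SAP 5.2.1.2 words it for the averaged 4-weekly analyses.

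State how a zero reference mean is handled under both versions. As it stands, a percentage increase from zero is undefined, and the form use ≥ 1.5 × mean would count a day of no use after a week of no use (0 ≥ 0).

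The cost is one derivation and one display, with no new data. The fixed-baseline version will not match the eDiary alert wording, and it rests on a single run-in week for the whole of Part C. The double counting at low reference use remains under either version and should be acknowledged. The change concerns the endpoint derivation only; the eDiary safety alert is not affected.
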